Participants will be randomly assigned to one of the three conditions: (1) Black-White, (2) Black-Black, and (3) White-White. In all conditions, infants will first view familiarization then test trials. In the familiarization trials, infants will begin by viewing four trials of familiarization. The familiarization trials will consist of two female actors facing forward and talking about infant-friendly topics like the weather, grocery shopping, school, or stars in a neutral-positive speech. The order in which actors speak and their pairings will be counterbalanced across participants. Each trial will last 10.5 seconds and be repeated four times. After familiarization, infants will view six test trials. Three of these test trials will be affiliation trials and three will be disengagement trials. In the affiliation trial, the two actors start by facing forward, turn to face each other, and then wave at each other saying “Hi!”, while smiling. In the disengagement trial, the actors start by facing forward, turn to face each other, and then make a “Hmph!” sound and turn their backs to one another. Both types of trials have the same overall length of the interaction and the actors maintained the same distance from each other throughout the trial so that they were the same distance apart during both affiliation and disengagement. Each test trial will last 3 seconds, with a still image of the actors for 15 seconds after the trial ends. Each test trial therefore will last 18 seconds. This length is in line with the maximum 20 second test trial used by the case study on Lookit (Scott et al., 2017). The affiliation and disengagement trials will be presented in an alternating order and the order will be counterbalanced across participants. Looking time at the still images will be measured at each trial. After completing the trials, parents will complete a survey that asks basic demographic information and provided an option to complete an additional, optional social network questionnaire. In this demographic survey, parents will provide racial, ethnic, and linguistic information about themselves and their infants, as well as questions about their neighborhood trust and zip code in which the infant resides. Parents will also have an option to complete a

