social network questionnaire about the people the infants see and interact with on a weekly and daily basis in the past month. Racial, ethnic, and linguistic demographic information about these individuals will be collected. Describe in detail below in *Measured variables* section.

Participants will be compensated \$5 (gift card) within approximately a week for their participation. If they complete the optional additional survey on infants' social network, they will be compensated an additional \$5. To be eligible for the gift card, the infant must be in the age range of the study (i.e., 8 months; 1 day – 15 months; 1 day) and the parent must provide and submit a valid consent statement. We will still provide compensation for the family even if they do not finish the study or we cannot use the infant's data.

Data will be excluded if we observe any parental interference during the study. We will include data as long as infants complete at least one affiliation and one disengagement trial to maximize including data as much as possible.

Measured variables.

We will use the following outcome variables: (1) Looking time during familiarization: We will record looking times during each 4 familiarization trials per infant. (2) Looking time during test trials: We will record the looking times during each 3 affiliation trials and 3 disengagement trials for each participant.

Demographic variables: (1) Infant race/ethnicity: One or more of the following categories can be used by the parent to identify their infant's race/ethnicity: American Indian or Alaska Native, Asian, Black or African American, Hispanic or Latino, White, Native Hawaiian or Other Pacific Islander, Other (which parents can specify any other race/ethnicity) (2) Infant language exposure: parents can select from the following categories: monolingual, exposure, bilingual/multilingual. Parents will also be asked to indicate what language(s) their infants are exposed to. (3) Parent education level: This will consist of 8th grade or less, 9th-12th grade no diploma, High school graduate or GED completed, Some college credit but no degree, Associate degree (AA, AS), Bachelor's degree (BA, BS, AB), Graduate or professional degree.

Exploratory variables: These measures were collected to explore questions about how infants' social environments may potentially relate to infants' looking patterns.

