Preliminary analyses. To check that attention during familiarization do not differ according to condition: A mixed ANOVA with trial number (first, second, third, and fourth) as a within-subjects factor, and condition (White-White, Black-Black, and Black-White), infants' age, and infants' sex as between-subjects factors will be run on looking time during familiarization. We predict that infants' attention will decrease as trial number increases in familiarization but no difference across conditions. To check that trial order, infants' age, and infants' sex does not influence infants' attention during test trials: A mixed ANOVA with test trial order (affiliation first or disengagement first), infants' age, and infants' sex as between-subject factor will be conducted. We do not expect any significant effects from these preliminary analyses as previously found in (Lieberman et al., 2017a). However, if any of the above factors are significant in relation to test trial looking time, we will include them as covariates in the following main ANOVA model.

Main analyses. A mixed ANOVA with condition (White-White, Black-Black, and Black-White) as a between-subjects factor and test trial number (first, second, or third) and test type (affiliation vs. disengagement) as within-subjects factors on the dependent variable of looking time during test trials will be conducted. If there is a significant interaction, each condition will be analyzed separately by performing the same repeated-measures ANOVA on test trial looking times for each condition with trial number and test trial type as within-subject factors.

References:

- Kelly, D. J., Quinn, P. C., Slater, A. M., Lee, K., Gibson, A., Smith, M., Ge, L., & Pascalis, O. (2005). Three-month-olds, but not newborns, prefer own-race faces. *Developmental Science*, 8(6), F31–F36. <https://doi.org/10.1111/j.1467-7687.2005.0434a.x>
- Kinzler, K. D., Dupoux, E., & Spelke, E. S. (2007). The native language of social cognition. *Proceedings of the National Academy of Sciences*, 104(30), 12577–12580. <https://doi.org/10.1073/pnas.0705345104>
- Liberman, Z., Woodward, A. L., & Kinzler, K. D. (2017a). Preverbal Infants Infer Third-Party Social Relationships Based on Language. *Cognitive Science*, 41(S3), 622–634. <https://doi.org/10.1111/cogs.12403>

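### Test trials alternate in type, but no planned ANOVA names order × test type; a fall in looking within pairs would cost the key test some power, and the term costs one error degree of freedom

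*Combined protocol and SAP*

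**What the plan says.** Study Protocol, Methods, Procedure: each infant sees six test trials, three of each type. "The affiliation and disengagement trials will be presented in an alternating order and the order will be counterbalanced across participants". The six trials therefore form three pairs, and the starting type decides which type comes first in every pair. Balance of order within each condition is not stated.

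SAP, Preliminary analyses: the test-trial check opens "A mixed ANOVA with test trial order (affiliation first or disengagement first"), adds age, and closes "sex as between-subject factor will be conducted". It is called mixed, but no within-subjects factor and no interaction is named. The rule for carrying results forward is: "if any of the above factors are significant in relation to test trial looking time, we will include them as covariates". The plan expects nothing significant from these checks. The one decline it predicts is for familiarization, where "attention will decrease as trial number increases in familiarization but no difference across conditions".

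SAP, Main analyses: condition is the between-subjects factor, with "test trial number (first, second, or third) and test type (affiliation vs. disengagement) as within-subjects factors". After a significant interaction, "each condition will be analyzed separately by performing the same repeated-measures ANOVA on test trial looking times for each condition". Order is named in neither model.

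**The concern.** The alternating sequence ties test type to position within the pair, in opposite directions in the two order groups. Any drop in looking from the first to the second member of a pair becomes an order × test type effect. Trial number (first to third) takes the same value for both members of a pair, so it cannot remove the shift. If order × test type is not in the model, the shift goes into the error for condition × test type, which tests the study's question, and into the error for each condition's own test-type effect. The conditional rule helps only if the preliminary check looks at the interaction and order then enters crossed with test type.

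**Working it through.** **Inputs.** From the documents: three conditions, six alternating test trials, and the models above. They give no planned N, SD, effect size or test-trial decline, so there is no power figure to reproduce. The nearest to a sample size is the laboratory's throughput of 100 to 150 infants a year. Assumed: alpha 0.05; 40 infants per condition (N = 120); infant SD 2.5 s, type-slope SD 1.5 s, residual SD 3 s; an effect of 1.5 s in Black-White only; complete trials; d = 0.5, 1.0, 1.5 s.

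**Step 1: where the fall appears.** Give the two positions of a pair the effects 0 and −d.

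- Affiliation first: affiliation minus disengagement = 0 − (−d) = +d; mean over six trials = −d/2.
- Disengagement first: difference = −d − 0 = −d; mean = −d/2.

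The means agree and the differences have opposite signs. In simulation the order main effect was significant in 4.7–5.3% of runs, while order × test type was significant in 45%, 96% and 100% at the three values of d.

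**Step 2: error variance.** For an infant's mean affiliation minus mean disengagement, the variance is 1.5² + 2 × 3²/3 = 2.25 + 6 = 8.25. Condition × test type is a one-way F test on this score, with 2 and 120 − 3 = 117 df. With the term omitted and order balanced within condition, the expected error mean square is 8.25 + d² × 120/117:

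- d = 0.5: 8.25 + 0.26 = 8.51
- d = 1.0: 8.25 + 1.03 = 9.28
- d = 1.5: 8.25 + 2.31 = 10.56

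With the term it is 8.25 on 116 df. For Black-White against the two same-race conditions, multiply by 1/40 + 1/80 = 0.0375. This gives 0.348 at d = 1.0 and 0.396 at d = 1.5 (simulated estimates 0.347 and 0.396), against a simulated true variance of 0.316. The estimated error is too large, so the test is conservative. With random order, estimated and true variance agree (0.347 and 0.351 at d = 1.0), but both are larger.

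**Step 3: omnibus power for condition × test type, without / with the term** (8000 runs per setting; standard error near √(0.66 × 0.34/8000) = 0.005).

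| Order allocation | d = 0.5 | d = 1.0 | d = 1.5 |
|---|---|---|---|
| Balanced within condition | 0.650 / 0.665 | 0.594 / 0.651 | 0.532 / 0.664 |
| Balanced overall only | 0.653 / 0.666 | 0.617 / 0.661 | 0.547 / 0.665 |
| Random | 0.653 / 0.660 | 0.604 / 0.655 | 0.558 / 0.661 |

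Exact noncentral-F power with the term is 0.661. Type I error without the term is 0.046, 0.037 and 0.023 when order is balanced within condition, and 0.047–0.054 otherwise.

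**Step 4: one-condition follow-up, order balanced:** 0.894 / 0.898, 0.869 / 0.889 and 0.840 / 0.896.

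**Step 5: sensitivity of the omnibus loss, in points, at the three values of d.**

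- Residual SD 4 s: 1.0, 3.7, 8.9. Residual SD 5 s: 0.5, 2.3, 5.1.
- Infants stopping early, which matters because data are kept "as long as infants complete at least one affiliation and one disengagement trial": 30% stopping, 0.7, 3.6, 8.0; 50% stopping, 0.7, 2.6, 5.5.
- Fall only between pairs (2 s per pair): 0.662 / 0.661, no loss.

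**Step 6: scale-free check.** Let r be d divided by the SD of the difference score. Starting from 80% power at r = 0, omitting the term gives 79.6% at r = 0.1, 77.3% at 0.25 and 69.6–69.8% at 0.5, for N from 60 to 150. Here r = d/√8.25 = d/2.87, so d = 0.5, 1.0, 1.5 correspond to r = 0.17, 0.35, 0.52. The two calculations agree.

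**Step 7: the conditional rule.** If only the order main effect triggers inclusion, power is 0.650, 0.597 and 0.539, essentially that of omitting the term. If the check includes test type and order enters crossed with it, power is 0.663, 0.651 and 0.664, the same as always including it.

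**The case against.** The plan names no interaction anywhere. Condition × test type is itself understood only because a factorial ANOVA conventionally contains its interactions. By the same convention, a mixed check on test trials must have a within-subjects factor, test type is the natural one, and order would enter the main model crossed. Step 7 shows that nothing is then lost, which would leave only unclear wording. The size also rests on assumed inputs. With a linear decline, d = 1.0 means 5 × 1.0 = 5 s over the six trials and d = 1.5 means 7.5 s, against a 15 s still image. With a fall after the first trial only, d is one third of that fall, so these values need drops of 3 s and 4.5 s. There is no inflated Type I error and no bias over allocation.

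Most of this stands: the size is unknown, the larger values of d are steep, and validity is not at issue. What does not follow is that the plan can stay as it is. A between-subjects check with order added as an uncrossed covariate fits the text at least as well, and under that reading the rule does not detect the shift. The pairing is created by the design, so its term should not wait on a significance test.

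**Conclusion.** The concern holds as a point of efficiency. On the text as written, a within-pair fall in looking can remain in the error of the key test and of the follow-ups. Under the stated assumptions the omnibus loss is about 1 point at d = 0.5 s, 4–6 at 1.0 s and 10–13 at 1.5 s. It is smaller with noisier looking or early stopping, and zero if looking falls only between pairs. The test is conservative if order is balanced within condition and holds its level otherwise. With random order, imbalance within a condition adds a chance shift to that condition's test-type effect, with SD d/√40 = 0.16d (0.16 s at d = 1.0); this is not a bias over allocation. Confidence in the size is medium, because N, the SDs, the effect and d are all assumed. The change is worth making because it costs so little.

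**What to change.** - Include order and order × test type in the main ANOVA and in each by-condition ANOVA, whatever the preliminary result.
- Name test type as a within-subjects factor in the preliminary test-trial ANOVA, and treat that ANOVA as descriptive for order.
- State that order is counterbalanced within each condition.

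The cost is SAP wording plus one error degree of freedom: 117 to 116 for condition × test type at the assumed N, and 39 to 38 in each follow-up. With no fall at all, omnibus power changes by 0.4 points or less at 40 per condition. At 20 per condition with order balanced only overall, a simulation gave 0.798 without and 0.787 with the term, a further reason to balance within condition. Crossing order with condition as well takes three degrees of freedom (117 to 114). That costs nothing if order is balanced within condition and about 1.5 points if order is random; it is not needed for this purpose.

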Study Protocol and Statistical Analysis Plan**Title of study:** Babies' Expectations About Racial Interactions**NCT number:** NCT05324007**Date of document:** May 31, 2022

Table of contents

| | Page Number |
|--------------------------------|-------------|
| Study Protocol..... | 3 |
| Objectives..... | 3 |
| Design..... | 3 |
| Methods..... | 3 |
| Statistical Analysis Plan..... | 6 |
| References..... | 7 |

Study Protocol

Objectives: The ability to categorize people into social groups is thought to arise early in human development (Liberman et al., 2017b). Language and race are often considered salient social categories that adults use to categorize and discriminate people. Infants also use language as a meaningful and inductive category: extensive research indicates that infants show preferences based on language (Kinzler et al., 2007; Pun et al., 2018) and infer communicative and social relationships based on language groups (Liberman et al., 2017a). In contrast, less is known about whether infants use race as a meaningful social cue. Past research has focused on infants' perceptual categorization skills that suggest infants can use race to make perceptual distinctions: For example, at 3 months of age, infants prefer to look at faces of people from their own-race (or races they are familiar with) over other-races (or races they are not familiar with) (Kelly et al., 2005). However, less is known about whether infants use race as an inductive social category. The current study therefore examines whether infants use race to predict social relationships as they do for language.

In the following, racial outgroup individual indicates an individual who is of a race that is different from the races of the infants' primary caregivers or parents. Racial ingroup individual indicates an individual who is of the same race as the infants' primary caregivers/parents.

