Design: The study will be conducted online on a platform called Lookit (lookit.mit.edu), in which participants can log on to this website to complete the study. The study will last about 10 minutes with parents providing consent via recorded videos, having their infants watch video stimuli, and then completing a demographic questionnaire after their infants finish watching the video stimuli. While infants watch the video stimuli, they are recorded via a webcam that is safely stored and accessible only by researchers. See <https://lookit.readthedocs.io/en/develop/index.html> for more details about this online platform.

The design of the study is based on Liberman et al. (2017a) but adapted for an online format. Infants will be randomly assigned to one of three conditions: (1) Black-White, (2) Black-Black, and (3) White-White. Black-White condition will consist of one White female and one Black female individual. White-White condition will consist of two White female individuals and Black-Black condition will consist of two Black female individuals. In total, there are four different White and three different Black actors. The pairings between the two actors will be counterbalanced across infants such that each actor will be presented in all conditions.

Methods:

Sample & recruitment. We will recruit infants between the age of 8 months;1 day to 15 months;1 day. No participant will be excluded on the basis of sex/gender or race and ethnicity. All participants – regardless of sex/gender, race, and ethnicity – will be randomly assigned one of the three conditions. Participants will be recruited from the Lookit participant database, in which families have voluntarily signed up to be contacted for studies in which their children are eligible for on the the platform. In addition, we will recruit from an existing University of Chicago Center for Early Childhood Research (CECR) participant pool (<http://babylab.uchicago.edu>). The participant pool has over 4000 children that range in age from birth to school age. Currently,

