the participant pool has 76 eligible infants in our targeted age range, but infants are consistently aging into this age range and year-round recruitment efforts are conducted such that typically our laboratory have successfully completed testing of 100 to 150 infants within a year. We have a strong track-record of recruiting and testing infants from racially and linguistically diverse backgrounds. Participants are typically contacted through phone or email by trained research assistants to participate in the study. Recruiting from these established participant pool typically results in ~50% inclusion of females. The racial and ethnic composition of the sample is expected to reflect the composition of the U.S. To ensure we continue to recruit a representative percentage of minority children, we will carefully monitor enrollment and include more recruitment efforts to cater to minority children as needed.

Procedure. Parents who have indicated they are willing to be contacted for studies from the database with infants in the eligible age range will be emailed a link to the study to participate. The parents can then click on the link and follow the instructions on screen to read about the description of the study and a consent document. If the parents decide to participate, they will be instructed to read the consent form and provide online permission by recording a video of themselves reading a statement, “I have read and understand the consent document. I am this child’s parent or legal guardian and we both agree to participate in this study.” Because the infants are not able to provide assent, no assent was obtained. Parents will have the option to download and/or print the forms to retain a copy for their files. Only participants with a valid consent will be permitted to participate in the study.

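### The SAP does not say which interaction triggers the per-condition ANOVAs, and no planned analysis after the omnibus test compares the conditions with each other

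*Combined protocol and SAP*

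**What the plan says.** Under Main analyses, the SAP specifies "A mixed ANOVA with condition (White-White, Black-Black, and Black-White) as a between-subjects factor" with "test trial number (first, second, or third) and test type (affiliation vs. disengagement) as within-subjects factors on the dependent variable" of test-trial looking time. The next step is: "If there is a significant interaction, each condition will be analyzed separately by performing the same repeated-measures ANOVA on test trial looking times". The within-condition ANOVAs use trial number and test type only. The SAP does not say which interaction it means, and it states no comparison of one condition with another.

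The Objectives section gives the question: "The current study therefore examines whether infants use race to predict social relationships as they do for language". The Design section sets one mixed pair against two kinds of same-race pair: "White-White condition will consist of two White female individuals and Black-Black condition will consist of two Black female individuals". The Objectives section also defines ingroup relative to the family: "Racial ingroup individual indicates an individual who is of the same race as the infants", with the sentence going on to refer to the caregivers or parents.

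**The concern.** With three factors there are four interactions: condition x test type, condition x trial number, test type x trial number, and the three-way term. The objective concerns whether the affiliation-minus-disengagement difference varies by condition. Condition x test type tests that directly. Condition x trial number and test type x trial number do not, yet as worded either one triggers the follow-up.

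Once triggered, the follow-up gives three separate test-type results. A difference in significance between conditions is not a significant difference between conditions. With modest groups and the same true effect in each, a mixture of significant and non-significant results is likely.

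There is a second gap when condition x test type is itself significant. Two degrees of freedom over three conditions show that the conditions differ somewhere. They do not show whether Black-White stands apart or whether White-White and Black-Black differ from each other. The plan has no contrast that tells these apart.

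**Working it through.** **Inputs.** The documents give no target sample size, alpha, effect size or power, so there is no figure to reproduce. The only guide to size is in Methods, Sample & recruitment: "typically our laboratory have successfully completed testing of 100 to 150 infants within a year". Assumed: alpha 0.05; n = 33, 40 or 50 per condition (N = 99, 120, 150); equal groups; complete data; no covariates. Effects are in SDs of the per-infant affiliation-minus-disengagement difference. The true effect is 0.3 SD in every condition, so there is no race effect, and it does not drift over trials.

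**Step 1. How often is the follow-up triggered with no true interaction?** Treating the four tests as independent, 1 - 0.95^4 = 18.5%. With one named trigger it is 5%.

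**Step 2. How often is the per-condition pattern mixed (one or two of three significant)?** Per-condition power p comes from the noncentral t distribution with n - 1 df and noncentrality 0.3 x sqrt(n). The mixed probability is 1 - p^3 - (1 - p)^3. Subtract the share in which condition x test type is also significant (simulated).

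| n | p | mixed | minus condition x test type significant | remainder |
|---|---|---|---|---|
| 33 | 0.3867 | 0.711 | 0.049 | 0.662 |
| 40 | 0.4565 | 0.744 | 0.051 | 0.693 |
| 50 | 0.5477 | 0.743 | 0.049 | 0.694 |

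**Step 3. Multiply the remainder by the chance that another interaction triggers the follow-up.**

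| Trigger reading | Chance | n = 33 | n = 40 | n = 50 |
|---|---|---|---|---|
| Any of the other three | 1 - 0.95^3 = 0.1426 | 9.4% | 9.9% | 9.9% |
| Only those involving condition | 1 - 0.95^2 = 0.0975 | 6.5% | 6.8% | 6.8% |
| Condition x trial number only (three-way treated as relevant) | 0.05 | 3.3% | 3.5% | 3.5% |

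Simulation of the full mixed ANOVA (60,000 runs per cell, compound symmetry) gives 9.5%, 10.1% and 10.0% for the first row and 6.4%, 6.8% and 6.9% for the second. For the third, a 20,000-run simulation that also required the three-way term to be non-significant gives 3.2%, 3.3% and 3.4%.

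**Step 4. Sensitivity.** On the literal reading, common effects from 0.2 to 0.5 SD give 2.3% to 10.1%; a full null gives about 1.4%. If the test-type effect drifted over trials identically in every condition (assumed +0.4, 0, -0.4 cell SD), the literal rate would be 40% to 70% for effects of 0.3 to 0.4 SD and 20 to 50 infants per condition. That increase comes through test type x trial number, so it does not arise if the trigger must involve condition.

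**Step 5. Precision of the missing contrasts.** Black-White minus the mean of the same-race conditions has variance 1/n + (1/4)(2/n) = 1.5/n in SD units. White-White minus Black-Black has variance 2/n. Half-width = t(0.975, N - 3) x sqrt(variance).

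- N = 99: 1.985 x sqrt(1.5/33) = 0.42; 1.985 x sqrt(2/33) = 0.49
- N = 120: 1.980 x sqrt(1.5/40) = 0.38; 1.980 x sqrt(2/40) = 0.44
- N = 150: 1.976 x sqrt(1.5/50) = 0.34; 1.976 x sqrt(2/50) = 0.40

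Infants with incomplete test trials, whom the protocol keeps, and covariates that the preliminary analyses may add are not modelled.

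**The case against.** The strongest reply is that the plan does test the race question. Condition and test type are both in the main model, so their interaction is a prespecified between-condition test, and an omnibus interaction followed by simple effects is a recognised approach. That stands. A reader might infer that a race effect could be claimed with no test of it anywhere; the documents do not support this.

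A second reply is that splitting by condition makes sense only for an interaction that involves condition, and that the three-way term bears on the question because it asks whether the test-type pattern over trials differs by condition. This is fair. It is why 3.5% to 7% is the main range and 10% belongs to the most literal reading. The 0.3 SD effect is also close to the least favourable value in the range tried.

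A third is that no figure here counts wrong conclusions. To reach one, the analysts would have to pass over a non-significant condition x test type result in their own table, and nothing says that they would. That stands too. The drift figures likewise should not be read as a forecast: the SAP expects that "attention will decrease as trial number increases in familiarization but no difference across conditions", which concerns overall attention in familiarization, not a test-type effect that changes over test trials.

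The per-condition ANOVAs do estimate the test-type difference in each condition. What remains missing is a formal comparison between conditions with an interval.

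**Conclusion.** The point holds as a gap in the decision rule. The trigger is unnamed, the relevant interaction need not be significant before per-condition results are read, and no planned contrast interprets it when it is significant. This follows from the SAP's wording and does not depend on any assumed number. The rates in the working illustrate the exposure under assumed alpha, group size and effect; they are pattern rates, not estimates for this study.

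A reader might go further and infer that a Black-White contrast should replace the omnibus test. The documents do not support that. Cross-race versus same-race is an inference from the three conditions. Because ingroup is defined by caregiver race, one same-race pair may be ingroup and the other outgroup for a given infant, and the two need not behave alike. Power also cuts both ways at N = 120: about 88% for the contrast against 80% for the omnibus if the same-race conditions are alike, but 25% against 62% if only White-White differs, by 0.5 SD. The absence of a stated direction for the test trials is missing detail and not part of this point.

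**What to change.** Amend Main analyses as follows.

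- Name condition x test type as the test of the objective and as the interaction that triggers follow-up. Keep it as the 2-df omnibus test.
- From the same fitted model, report two contrasts of the affiliation-minus-disengagement looking-time difference, each in seconds with a 95% CI: Black-White minus the mean of White-White and Black-Black, and White-White minus Black-Black. Use them to interpret the omnibus result.
- Label the per-condition ANOVAs descriptive.

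The cost is a few lines of SAP text and two extra estimates; no new data are needed. The intervals would be fairly wide, so the contrasts may leave the pattern unsettled. Trial-number interactions would no longer open the follow-up, though they can still be reported. The contrasts do not use caregiver race, so they would not resolve ingroup versus outgroup for individual infants.
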